10.5.5 Secondary Analysis

EA-SCD PRO's will be analyzed quantitatively using linear mixed models for repeated measures. The models will include fixed factors for baseline scales, the site size stratification factor, treatment arm, assessment time point, and the treatment arm by time point interaction. Random factors will include investigational site and subject within site to account for correlation in responses within individual sites and within the same subject. Model-based estimates of PRO scores will be used to estimate percentage change between the treatment arms. Additionally, PRO will be analyzed using survival analysis techniques. For each EA-SCD participant, the time from baseline to a 10% worsening (TTW) in the scale will be calculated. For EA-SCD participants not experiencing a 10% worsening, TTW will be censored at the last patient reported outcome assessment. TTW will be analyzed using Kaplan-Meier techniques and Cox proportional hazards models. The

proportional hazards models will include the same factors as described for the primary analysis. Planned sensitivity analysis will be conducted to evaluate time to worsening for worsening thresholds ranging from 10% to 30%. The repeated measures and survival analyses of the EA-SCD PRO's will also include supportive and sensitivity analyses to account for potential baseline confounders as previously described in the primary analysis. EA-SCD satisfaction with transition services will be summarized descriptively.

Intervention fidelity will be analyzed descriptively. A CONSORT-type diagram will be provided, including a summary of all mentors who consented, had a background check, passed the background check, completed practice call 1, completed Peer Mentor University online training, completed practice call 2, and were matched with at least one EA-SCD. Timelines for mentors and EA-SCDs on the PM arm will be summarized descriptively. Frequency of mentor contacts will be analyzed descriptively in terms expected contacts per protocol versus actual. This will include calls placed (mentor to EA-SCD), calls answered (EA-SCD to mentor), messages sent (mentor to EA-SCD), and messages received (EA-SCD to mentor).

ST3P UP application usage will be analyzed descriptively in terms of number of contacts between study subjects and transition coordinators, transition coordinators and PIs, and between PIs. Additionally, the use of education resources in the application will be summarized descriptively for the study subjects. Associations between EA-SCD outcomes (particularly acute care utilizations) and contact frequency, will be analyzed similarly to the methods described above for the primary analysis, with treating the app usage as a continuous covariate. Additionally, application usage will be correlated with EA-SCD PROs (specifically TIP-RFT assessments) similarly to the methods described above, treating the app usage as a continuous covariate. For the analysis described about regarding application usage, this will be done in two ways: (1) including all subjects and, for subjects who did not use the application, usage would be equal to zero; (2) only including the subset of subjects who used the application and looking at the impact of amount of usage on outcomes.

Composite QI-validated scores of the Six Core Elements provided by the sites in 6-month intervals will be analyzed using linear mixed models for repeated measures. One goal of the QI analyses is to assess the convergence in scores between pediatric and adult practices. This will be accomplished with a model that includes baseline QI score, clinic (pediatric versus adult), time, and the provider by time interaction as fixed factors. Site will be included as a random factor to account for repeated observations over time. Importantly, the type of provider will also be evaluated. This will be accomplished using a similar model as described above but will use provider type: Pediatrician to Pediatrician; Pediatrician to Internist; Pediatrician to Med/Peds Specialist, Med/Peds specialist to Med Peds specialist as the treatment factor. Additionally, composite QI-validated scores will be compared with site self-reported scores for concordance over time. Provider satisfaction with transition services will be summarized descriptively.

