STATISTICAL CONSIDERATIONS	Estimated average acute care utilization rate for EA-SCD is 6 visits / year. This study is designed to detect a 20% reduction in the number of acute care encounters per year which is considered clinically significant to our patient stakeholders. Based on a two- sided alpha = 0.05 significance level, 67 subjects per arm would provide approximately 85% power to detect a 20% reduction in the number of acute care utilizations under individual randomization, assuming the number of encounters follows a Poisson distribution for rare events. Sample size was inflated based on the cluster size coefficient of variation among our 14 participating clinical sites (55%) and the intra-class correlation (ICC) assumed to be 0.05. Based on these parameters, 183 subjects per arm (366 total subjects) will retain approximately 85% power. The sample size was increased to 537 total EA-SCD subjects to account for potential missing data and allow for robust evaluation of secondary endpoints. It is estimated that this can be accomplished with an enrollment rate of 35% of the EA-SCD patient population.
NUMBER OF EA-SCD PARTICIPANTS	537 total participants will be enrolled Each arm will enroll approximately 269 EA-SCD aged 16 – 25 years
NUMBER OF CLUSTERS	There will be 14 cluster sites, each cluster site comprised of a pediatric SCD clinic, an adult SCD clinic and a SCD CBO. There are 8 large cluster sites with ≥40 EA-SCD currently in pediatrics and 6 small cluster sites with <40 EA-SCD currently in pediatric care. Based on self-reported enrollment targets from each site, 80% of participants will come from large clusters.

SCHEMA

[figure not shown]
Study Schema Figure 1: Overview of Study Design

	Study Schema										
Practices with Emerging Adults with SCD (EA-SCD) aged 16 - 25y Randomized at the Practice Level											
Small Sized Program [≤ 40 EA-SCD] Large Sized Program [> 40 EA-SCD]											
Arm 1- A	Arm 1- B	Arm 2-A	Arm 2-B								
Structured Education Based Transition Program [STE]	Structured Education Based Transition Program [STE] + Peer Mentoring [STE + PM]	Structured Education Based Transition Program [STE]	Structured Education Based Transition Program [STE] + Peer Mentoring [STE + PM]								
	Outcome Meas	ures at 24 Montl	ns								
Primary Outcome: Cha		are visits [ED visits, Adm Hospital Days]	issions, Readmissions at 14d,								

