5.3.6 Health Care Transition (HCT) Process Measurement Tool

To determine the level of improvement in a practice with adherence to the Six Core Elements, each pediatric and adult practice will be scored according to whether some or all of the implementation steps have been completed using the HCT Process Measurement Tool developed by GotTransition.org. Scores for each step will vary depending on complexity or importance. Each practice will be scored every six months to determine the degree to which they move closer to adherence to the desired standardized clinical practice pattern.

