10.2 Sample Size and Accrual

Sample size calculations are based on the primary endpoint of acute care utilization visits per year (at the EA-SCD participant level). Utilizing a randomized cluster design, seven clinical sites will be randomized per arm. The sample size calculation strategy is to calculate the required minimum sample size based on an individual patient randomized design, and then inflate the sample size based on cluster randomized considerations.⁵⁴ A conservative estimate of the average acute care utilization rate for EA-SCD is 6 acute care visits per year based on data for North Carolina reported by the RuSH population surveillance project.⁴ In South Carolina, the acute care utilization rates among 18-30 y with SCD was reported as 7.17 (95% CI 6.34-7.99).55 At Atrium Health (formerly known as Carolinas Healthcare System), 295 EA-SCD had 1972 emergency department visits and 221 hospital admissions in 2015 with an average acute care

utilization rate of 6.82 visits per year. This study is designed to detect a 20% reduction in the number of acute care encounters per year (assuming a base case of 6 encounters). A 20% reduction in acute care utilization is considered clinically significant based on patient partners reporting that 1 less acute care visit a year is meaningful. Based on a two- sided alpha = 0.05significance level, 67 EA-SCD participants per arm would provide approximately 85% power to detect a 20% reduction in the number of acute care utilizations under individual randomization, assuming the number of encounters follows a Poisson distribution for rare events. The sample size will be inflated based on two parameters: the cluster size coefficient of variation and the intra-class correlation (ICC).⁵⁴ The cluster size coefficient of variation observed among the 14 participating clinical sites is 55%. Therefore, the coefficient of variation is assumed to be 60% and the ICC is assumed to be 0.05.⁵⁶ Based on these parameters, a minimum of 183 EA-SCD participants per arm (366 total EA-SCD participants) will retain approximately 85% power. To account for potential missing data and allow for robust evaluation of secondary endpoints the sample size will be increased to a total of 537 EA-SCD participants. It is estimated that this enrollment can be accomplished with an enrollment rate of 35% of the EA-SCD patient population.

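### The repeated-measures PRO model has no site-by-time random effect, so arm-by-time tests and between-arm differences in change are anti-conservative if site effects drift

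*Combined protocol and SAP*

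**What the plan says.** Section 10.5.5 analyses the PRO scales with linear mixed models for repeated measures. The fixed part holds the baseline score, the site-size stratum and "treatment arm, assessment time point, and the treatment arm by time point interaction". The random part is: "Random factors will include investigational site and subject within site to account for correlation in responses within individual sites and within the same subject".

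Sections 10.5.4 to 10.5.6 give the PRO models no site-by-time effect, site-level slope, cluster-robust variance or small-sample degrees-of-freedom method. The mentor-clustering sensitivity analysis in 10.5.4 is set against the primary analysis and does not fill this gap. The stated use of the PRO model is to estimate percentage change between arms from model-based scores. No test of the interaction is named.

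Allocation is by site: "seven clinical sites will be randomized per arm" (10.2). PROs are collected every six months from enrolment (6.4.4). The minimum follow-up of 6 pediatric plus 24 adult months (Section 5) therefore gives five follow-up assessments. On site-level change, 5.3.6 says: "Each practice will be scored every six months to determine the degree to which they move closer to adherence".

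**The concern.** A random site effect that is constant over time protects a comparison of arm means. It does nothing for a comparison of arm trajectories, because it subtracts out. What remains is participant residual error, as if roughly 269 participants per arm had independent time courses. If participants at one site share a movement in scores between visits, that movement belongs in the error term for a site-randomized comparison.

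The protocol gives reasons to expect such movement:

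- Sites roll out the transition programme over 18 to 24 months (1.2, Section 5), and 5.1.2 plans to separate sites by adherence at 24 months.
- Participants leave the site's pediatric clinic for its adult clinic 6 to 12 months after consent (3.2.1). Any gap between the two clinics becomes a site-specific change over follow-up.
- Sites may substitute their own education module (6.3, footnote e).

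At stake is a false claim on a secondary objective (2.2.1): a few sites with smoother transfers could be reported as a mentoring benefit.

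**Working it through.** **The plan's own figure.** The only sample-size figures concern acute care visits, and they reproduce. For the 20% reduction from 6 to 4.8 visits, n = (1.960 + 1.036)² × (6 + 4.8) / 1.2² = 67.3 per arm. Power at 67 is 84.8%, against the stated "67 EA-SCD participants per arm would provide approximately 85% power to detect a 20% reduction in the number of acute care utilizations". Inflating for 7 sites per arm, with ICC 0.05 and cluster-size variation 60% (10.2): 67 × 7 × 0.95 / (7 − 67 × 0.05 × 1.36) = 445.55 / 2.444 = 182.3, so 183 per arm. No corresponding ICC, power or error rate is given for any PRO.

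**Inputs for the PRO check.**

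- From the documents: 14 sites, 7 per arm; 537 / 14 ≈ 38 participants per site; five follow-up visits; two-sided 5% (stated for the primary endpoint only).
- Assumed: variances of 0.05 for site, 0.50 for subject and 0.44 for residual. Site-by-time variance s is 0.005, 0.01 or 0.02, about 0.5%, 1% and 2% of the total. Data are complete.

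**Single change contrast between two follow-up visits.** The true variance of a site's mean change is 2(s + 0.44/38). The listed random effects imply 2(s + 0.44)/38. The ratio is DE = 1 + 37s/(s + 0.44), and the rejection rate under no arm effect is 2Φ(−1.96/√DE).

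| s | DE | Change contrast | Arm-by-time F test (simulated) |
|---|---|---|---|
| 0 | 1.00 | 5% | 5% |
| 0.005 | 1.42 | 10% | 15% |
| 0.01 | 1.82 | 15% | 27% |
| 0.02 | 2.61 | 22% | 45% |

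Repeat simulations of the non-zero rows gave 14–15%, 27–28% and 45–46% for the F test. Tested against site-by-time variation, the rate returns to about 5%.

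**Unequal sites.** A second simulation used 537 participants, 8 large sites with 80% of them and 6 small ones, five visits, and 1,500 runs per setting. The F test matched a fitted mixed model with the listed random effects (1.2381 v 1.2382; 1.2335 v 1.2335). CAC is the correlation of a site's effect over time; the subject variance share was 0.45–0.65. Rejection rates for arm-by-time at ICC 0.05:

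| CAC | Independent deviations | Linear site trends |
|---|---|---|
| 0.95 | 9–15% | 12–16% |
| 0.9 | 16–25% | 18–28% |
| 0.8 | 29–43% | 28–39% |
| 0.6 | 49–64% | 42–53% |

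- The values of s above correspond to CAC 0.05/0.055 = 0.91, 0.05/0.06 = 0.83 and 0.05/0.07 = 0.71.
- At ICC 0.01–0.02 with CAC 0.9–0.95 and independent deviations, the rate is about 6–11%.
- At CAC 1.0 (no drift) it is 4.1–6.4% over all ICCs, close to nominal given a Monte Carlo standard error of √(0.05 × 0.95/1500) = 0.6%.
- Under linear trends the last-versus-first contrast is worse than under independent deviations: at ICC 0.05 and CAC 0.9, 25–34% against 10–15%.
- An unstructured within-subject covariance does not help (29.3% v 29.3% at ICC 0.05, CAC 0.8, subject share 0.45).
- With a site-level test (F on 4 and 48 df, or a site-slope t on 12 df) the rate is 3.3–6.2% in every setting.

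**Arm differences that keep the site effect.** In the balanced setting with the listed random effects and 12 df (14 sites − 2 arms), for s = 0.005, 0.01 and 0.02:

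- Arm effect averaged over visits: 5.1%, 5.2%, 5.3%.
- Arm difference at the last visit: 5.0%, 5.6%, 6.7% (4.8%, 5.3%, 7.3% if the site variance is 0.02).
- With a normal reference instead of 12 df, the last-visit rate is 7–10%, but it is already about 7% at s = 0. That part is a degrees-of-freedom matter.

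**The case against.** The strongest reply is that these error rates belong to a test the plan does not name. Section 10.5.5 lists the interaction as a fixed factor but commits only to between-arm estimates, and for those the site effect does most of the work. This stands. A reader might infer that all PRO treatment effects are inflated; the visit-averaged and single-visit figures show otherwise. The problem remains for the interaction and for differences in change, which this model would supply if they are reported.

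A reader might also infer that the test will reject far too often as a matter of course. The documents do not support that. They give no PRO site-by-time variance, and the ICC of 0.05 was set for acute care visits.

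Nor does the point reach every PRO. The transition feedback survey is a listed PRO (2.2.1, 10.3.2), but satisfaction with transition services is summarized descriptively. The time-to-worsening analyses use other models.

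The mechanism is also partly indirect. The six-monthly scores measure practice adherence, not PROs. Roll-out runs on study months while PRO visits run from enrolment, so staggered entry would spread a roll-out effect over several visits. That weakens the roll-out argument. It does not remove the pediatric-to-adult move, which is tied to each participant's own timeline.

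Finally, 38 per site at every visit is a target, and the synopsis says the mentoring comparator cannot be assessed quantitatively as planned. With 19 per site, DE = 1 + 18s/(s + 0.44) = 1.20, 1.40 and 1.78, and the change contrast rejects about 7%, 10% and 14%: smaller, but still above nominal.

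**Conclusion.** The structural gap is in the text: the PRO model includes arm-by-time but lists no random term for site-specific change. Its consequence is conditional. If site effects on a PRO drift, the arm-by-time test and between-arm differences in change are anti-conservative. At 0.5–2% assumed site-by-time variance, with full enrolment and complete data, the rates are about 15–45% and 10–22% against a nominal 5%. At low ICC with nearly stable site effects the excess is small, and at zero site-by-time variance there is none. Visit-averaged arm effects are essentially sound and single-visit differences nearly so (about 5–7%), given site-level degrees of freedom. The point covers secondary endpoints analysed with the repeated-measures model only. It should be fixed before analysis; it does not touch the primary endpoint.

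**What to change.** In 10.5.5, add a random site-by-time effect, or a site-level random slope, to the repeated-measures PRO models. Base arm-by-time, change and visit-specific inference on Kenward-Roger or Satterthwaite degrees of freedom. State in advance that if the model does not converge, site-level mean changes will be analysed instead. It would also help to say whether the interaction or a particular contrast carries the PRO conclusion.

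The cost is SAP wording, one extra variance component to estimate from 14 sites, and somewhat wider intervals for change contrasts. If there is no drift, the component should estimate near zero and little is lost.

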5.3.1 PedsQLTM Sickle Cell Disease Module

The **PedsQL**TM Sickle Cell Disease Module 3.0 comprises 6 domains and was derived from qualitative methods involving patient/parent interviews and expert opinion across multiple sites and has been validated for use in the evaluation of SCD specific health related quality of life in research and clinical practice.⁵⁰ This 43-item scale measured on a 5-point Likert-type scale shows excellent feasibility, excellent reliability for the Total Scale Scores (patient self-report $\alpha = 0.95$; parent proxy-report $\alpha = 0.97$), and good reliability for the nine individual scales (patient self-report $\alpha = 0.69$ –0.90; parent proxy-report $\alpha = 0.83$ –0.97).

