5.3.3 Sickle Cell Transition Intervention Program – Readiness for Transition (TIP-RFT) Assessment

The Sickle Cell **TIP-RFT** instrument was developed to provide a validated SCD specific readiness for transition assessment tool with established reliability for routine use in the clinical domain. ¹⁷ The current TIP-RFT has 4 subscales and 54 items that quantifies knowledge, skills and attitudes necessary for a successful transition from pediatric to adult care. ^{16,52} The domains assessed include knowledge and skills in medical self-care, social support, health benefits, independent living and educational/vocational skills. The TIP-RFT assessment will be used to guide interventions to improve transition readiness and can provide a foundation for future research on other variables that might be associated with transition readiness.

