5.3.4 Medical Outcomes Study – Social Support Scale (MOS-SSS)

The Medical Outcomes Study - Social Support Survey (MOS-SSS) was developed as a brief multidimensional social support survey for persons living with chronic illness. ⁵³ MOS-SSS assesses support ranked on a 5-point Likert-type scale along four dimensions, emotional /informational, tangible, affectionate, and positive social interaction, to give an overall functional social support index. ⁵³

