6.3 EA-SCD Participant Level Assessment Calendar

EA-SCD Participant Level Assessment Calendar																								
Study Month	Screening																							
	All Sites	Peer Mentor Sites Only	Baseline	3	6	9	12	15	18	21	24	27	30	33	36	39	42	45	48	51	54	57	60	Off Study
Eligibility Screening	•																							
Informed Consent / Assent	•																							
Demographics/Disease Characteristics ^a	•																							•
Mentor Matching ^b		● ^g																						
Acute and Ambulatory Care Visit Data Collection ^c			•	•	•	•	•	•	•	•	•	•	•	•	•	•	•	•	•	•	•	•	•	•
Transition Education Intervention Q3			• h	•	•	•	•	•	•	•	•	•	•	•	•	•	•	•	•	•	•	•	•	•
PedsQL-SCD Module			● h		•		•		•		•		•		•		•		•		•		•	•
MOS-SSS			● h		•		•		•		•		•		•		•		•		•		•	•
TIP-RFT			• h		•		•		•		•		•		•		•		•		•		•	•
ASCQ-ME QOC			• h		•		•		•		•		•		•		•		•		•		•	•
Health Care Transition Feedback Survey for Youth/Young			• h				•				•				•				•				•	•
ST3P-Up App	Downloade		Download	•	•	•	•	•	•	•	•	•	•	•	•	•	•	•	•	•	•	•	•	•

- a Demographic information collected at baseline will be re-assessed at end of study for updates and/or changes
- b During screening, EA-SCD subjects are required to provide their day/time availability for peer mentoring calls to facilitate mentor matching. These subjects MUST be matched to a mentor prior to administering baseline surveys
- c Ambulatory and acute care visits will be collected for the preceding 12 months (a month is defined, numerically, as 30.4375 days, and visit windows are based on the date of enrollment). Ambulatory visits will include visits within the healthcare setting, primary care visits, and virtual visits via telephone ONLY. Acute care visits may include, but are not limited to ED, urgent care, day hospitals, infusion centers, and hospital admissions.
- d Study visits will occur with a +/- 4 weeks window for q3mo visits. EA-SCD subject must be seen by their SCD provider during these visits. However, these visits may occur in other locations within the healthcare setting where SCD care is provided or virtually as long as required structured and targeted transition education is provided

Version 6: 12/22/2022

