10.3.2 Definition of Secondary Endpoint

Quantitative EA-SCD participant-reported outcome scores will be captured longitudinally for each subject. Data will be collected for each subject using the following scales:

- Adults Sickle Cell QOC Measure (ASCQ-ME QOC) for health-related quality of life
- PedsQLTM-SCD module for health-related quality of life
- Medical Outcomes Study Social Support Survey (MOS-SSS)
- Transition Readiness Score as measured by the TIP-RFT scale
- Health Care Transition Feedback Survey

Count variables capturing healthcare utilization will be calculated for each EA-SCD participant for the following variables. These will be annualized to 12-month and 24-month periods as described above.

- The number of ambulatory visits
- The number of visits with adult providers
- The number of hospitalization days
- 14-day and 30-day readmission rates

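### The only between-arm effect size named from the PRO mixed models is a percentage, which depends on each scale's scoring origin and is tied to no visit

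*Combined protocol and SAP*

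**What the plan says.** Section 10.5.5 sets an additive model: "EA-SCD PRO's will be analyzed quantitatively using linear mixed models for repeated measures". Its terms are listed as follows: "The models will include fixed factors for baseline scales, the site size stratification factor, treatment arm, assessment time point", and an arm-by-time interaction, with random effects for site and for subject within site. The between-arm summary drawn from it is one sentence: "Model-based estimates of PRO scores will be used to estimate percentage change between the treatment arms". The section does not mention an adjusted mean difference or a confidence interval for the PROs.

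On the scores themselves:

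- Section 5.3.1, PedsQL-SCD: "This 43-item scale measured on a 5-point Likert-type scale shows excellent feasibility".
- Section 5.3.4: "MOS-SSS assesses support ranked on a 5-point Likert-type scale along four dimensions".
- Section 5.3.3: "The current TIP-RFT has 4 subscales and 54 items that quantifies knowledge, skills and attitudes"; no response format is given. Section 5.3.2 gives none for ASCQ-Me QOC either.
- Section 10.3.2 defines the PRO endpoint: "Quantitative EA-SCD participant-reported outcome scores will be captured longitudinally for each subject". It then lists the scales, with no item coding, range, direction or zero point.

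On timing, the section 6.3 calendar schedules these four scales at baseline, every 6 months to month 60, and at off-study. Study Schema Figure 1 places change in PROs under the outcome measures at 24 months.

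Section 10.5.5 also defines time to a 10% worsening of each scale, with sensitivity thresholds from 10% to 30%.

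**The concern.** A percentage difference has a fixed meaning only when zero means none of the quantity. The primary endpoint meets that condition: it is a visit count analysed with a log link, so a relative effect is natural. A score built from 5-point items does not. Its lowest value is 1, 0 or something else according to the coding chosen, and the percentage follows that choice.

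Three choices are left open: the scoring origin and direction, the denominator, and the visit. Each changes the reported effect without changing the evidence. If they are settled after the data are seen, the size of the PRO effect is partly a reporting decision. PROs are the first secondary objective (section 2.2.1), so their effect sizes will be read closely.

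**Working it through.** The plan gives no PRO mean, SD, difference or power, so there is no stated figure to reproduce. All item means below are assumptions, chosen to show a range.

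**1. Algebra.** Take the percentage as P = 100 × (mPM − mSTE) / mSTE. Adding a constant c to every score gives P = 100 × (mPM − mSTE) / (mSTE + c): the numerator is unchanged and the percentage moves. Multiplying every score by k leaves P unchanged, because k cancels. So the origin matters and the unit does not.

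**2. Illustration.** Assume an arm difference of 0.2 item points. The 0-100 score is (item mean − 1) × 25.

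| Assumed item means on 1-5, STE+PM v STE | 1-5 coding | 0-4 coding | 0-100 |
|---|---|---|---|
| 2.0 v 1.8 | 0.2/1.8 = 11.1% | 0.2/0.8 = 25.0% | 5/20 = 25.0% |
| 3.0 v 2.8 | 0.2/2.8 = 7.1% | 0.2/1.8 = 11.1% | 5/45 = 11.1% |
| 4.0 v 3.8 | 0.2/3.8 = 5.3% | 0.2/2.8 = 7.1% | 5/70 = 7.1% |

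**3. Direction.** With STE 4.0 and STE+PM 4.2 on 1-5 coding, the percentage is 0.2/4.0 = 5.0%. Reverse-scored (6 minus the item mean), the same answers are 2.0 v 1.8, or −0.2/2.0 = −10.0%. The sign change is expected; the change in size is not.

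**4. Denominator.** The sentence could instead mean the arm difference in percentage change from baseline. With a common baseline item mean of 2.0 and the same 0.2 arm difference, that is 0.2/2.0 = 10.0 percentage points on 1-5 and 5/25 = 20.0 on 0-100. This reading depends on the origin as well.

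**5. Model check.** One data set was simulated with 14 sites, 38 participants per site and 4 visits. It was fitted with the fixed and random effects of section 10.5.5 and scored three ways. Results at the last visit:

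| Scoring | Adjusted difference | STE adjusted mean | Percentage | z |
|---|---|---|---|---|
| 1-5 | 0.2752 | 2.970 | 9.27% | 4.446 |
| 0-4 | 0.2752 | 1.970 | 13.97% | 4.446 |
| 0-100 | 6.8809 | 49.257 | 13.97% | 4.446 |

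The difference in points carries over exactly (0.2752 × 25 = 6.88) and the test statistic is identical. Only the percentage moves.

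**6. Time point.** Six-monthly visits to month 60 give 60/6 = 10 scheduled post-baseline visits. With an arm-by-time interaction there is one arm contrast per visit, and section 10.5.5 does not say which visit, or which average, yields the percentage.

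**7. The 10% worsening threshold.** From an assumed baseline item mean of 3.0, 10% is 0.3 item points on 1-5 coding. On 0-100 the same baseline is 50, and 10% is 5 points, or 5/25 = 0.2 item points. The event definition therefore also depends on the origin.

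**The case against.** The case for leaving the text alone has four parts.

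- **The instruments are established and cited.** If each manual fixes one scoring rule, each scale has one percentage. Appendix A holds the PedsQL forms, whose contents were not available here, so this cannot be settled. It would narrow the point without removing it: the percentage would still reflect a convention, and the plan's own text would still give no denominator or visit.
- **The sentence does not exclude reporting adjusted means or their difference.** That is fair. But no such measure is named, and the one that is named is the weakest available from this model.
- **The figures are illustrative.** They are. The 25.0% comes from a low assumed STE mean of 1.8, and the gap narrows as the mean rises.
- **Month 24 is itself a choice.** Transfer is planned 6 to 12 months after consent. If enrollment is close to consent, month 24 falls about 24 − 12 = 12 to 24 − 6 = 18 months after transfer, while follow-up runs to at least 24 months in adult care. It is still the outcome time that the schema gives.

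A reader might infer more: that the main result for every PRO is arbitrary, or that the PRO tests are unsound. The documents do not support either. Satisfaction with transition, the subject of the Transition Feedback Survey, is summarised descriptively. The PROs also have a planned time-to-worsening comparison, and nothing calls the percentage the main result. Only two instruments are documented as 5-point Likert-type, and the arm contrast and its test do not depend on the origin. Nor do the documents state how sparse the late visits will be; the supported point is only that no visit is named.

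**Conclusion.** The point holds as a clarification of effect-size reporting for secondary endpoints. The percentage named in section 10.5.5 is not determined by the plan's text, because origin, direction, denominator and visit are all unstated. In the central assumed case it is 7.1% or 11.1% for the same answers. Over the assumed means examined, the change of origin multiplies it by about 1.3 (7.1/5.3) to 2.3 (25.0/11.1).

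This rests on the plan's description of PedsQL-SCD and MOS-SSS. It extends to TIP-RFT and ASCQ-Me QOC if, as is likely but undocumented, their scores also lack a true zero. The primary endpoint, the arm contrasts and their tests are unaffected.

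**What to change.** Replace the percentage sentence in section 10.5.5 with wording such as:

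> For each PRO analysed by mixed model, the arm effect is the adjusted mean difference (STE+PM minus STE) in scale points at month 24 after enrollment, with 95% CI, on the scale's declared scoring range and direction. Any percentage is a labelled descriptive supplement, with its denominator stated.

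Add to section 10.3.2 one line per instrument giving item coding, score range and direction, with the scoring source cited. State that the 10% to 30% worsening thresholds are computed on that declared range. An SD-standardised difference may be added if a comparison across scales is wanted; it is optional.

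The cost is a few lines of SAP text. The fitted model, data collection and sample size do not change.
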